#### **12.3.1 Cumulative Serious Adverse Events**

- Cystoid macular edema
- Hypopyon
- Endophthalmitis
- Lens dislocation
- Pupillary block
- Retinal detachment
- Secondary surgical intervention

#### **12.3.2 Persistent Serious Adverse Events**

- Corneal stromal edema
- Cystoid macular edema
- Iritis
- Raised IOP requiring treatment

This list is consistent with the categories provided in I.S. EN ISO 11979-7:2014. A persistent AE is an AE that is present at the conclusion of a clinical investigation per I.S. EN ISO

11979-1. Any other potentially sight-threatening event may also be considered serious based on the judgment of the Investigator and must be reported appropriately as delineated in Section 12.6.

## **12.4 Terminology**

### **12.4.1 Adverse Device Effect**

An ADE is an AE related to the clinical investigation. This definition includes AEs resulting from insufficient or inadequate instructions for use, deployment, implantation, installation, or operation; any malfunction; and use error or intentional misuse of the device.

### **12.4.2 Serious Adverse Device Effect**

A SADE is an ADE that has resulted in any of the consequences characteristic of a SAE.

### **12.4.3 Anticipated Serious Adverse Device Effect**

An ASADE is a SADE which by its nature, incidence, severity, or outcome has been identified in the risk analysis report.

### **12.4.4 Unanticipated Serious Adverse Device Effect**

An USADE is a SADE which by its nature, incidence, severity or outcome has not been identified in the risk analysis report.

### **12.4.5 Device Deficiencies**

A device deficiency is an inadequacy of a medical device with respect to its identity, quality, durability, reliability, safety, or performance. This definition includes malfunctions, use errors, and inadequate labeling. Malfunction is defined as a failure of a medical device to perform in accordance with its intended purpose when used in accordance with the instructions for use or clinical investigation plan. Use error is defined as an act or omission of an act that results in a different medical device response than intended by manufacturer or expected by user; this includes slips, lapses, and mistakes. An unexpected physiological response of the subject does not in itself constitute a use error.

A device deficiency may or may not be associated with subject harm (ie, ADE or SADE); however, not all ADEs or SADEs are due to a device deficiency. The Investigator must determine the applicable category for the identified or suspect device deficiency and report any subject harm separately. Examples of device deficiencies include the following:

- Failure to meet product specifications (eg, incorrect IOL power,)
- IOL defect
- Broken IOL optic
- Broken IOL haptic
- Scratched IOL optic
- Unsealed device packaging
- Lack of efficacy
- Autorefractor errors and other diagnostic equipment related deficiencies

## **12.5 Return Product Analysis**

Study Sponsor representatives and their contact information are provided in the MOP that accompanies this protocol.

Alcon Products associated with device deficiencies and/or product related AEs must be returned as specified in the MOP and must include the Complaint # and which will be provided by the Study Sponsor.

## **12.6 Monitoring for Adverse Events**

At each visit, after the subject has had the opportunity to spontaneously mention any problems, the Investigator must inquire about AEs by asking the standard questions:

- “Have you had any health problems since your last study visit?”
- “Have there been any changes in the medicines you take since your last study visit?”

AEs must be reported for any clinically relevant change, in the opinion of the Investigator, in concomitant medication(s) that is the result of an untoward (unfavorable and unintended) change in a subject's medical health.

Changes in any protocol-specific ocular or systemic parameter evaluated during the study are to be reviewed by the Investigator. Any untoward (unfavorable and unintended) change in a protocol-specific parameter or questionnaire response that is clinically relevant, in the opinion of the Investigator, is to be reported as an AE. These clinically relevant changes will be reported regardless of causality.

## **12.7 Procedures for Recording and Reporting**

All AEs must be documented on the AE electronic case report form (eCRF) by the site and are monitored on a routine basis by the Study Sponsor.

AEs are collected from the time of informed consent. Any pre-existing medical conditions or symptoms present in a subject are not considered AEs in the study. Aqueous cells and flare, corneal edema, raised IOP and superficial punctate keratitis are examples of early postoperative findings that are typically observed following ocular surgery. These are not considered AEs if they can be reasonably expected to resolve within a week and not result in any untoward long term visual outcome impact.

The Investigator must promptly document all ADEs and SAEs with details including the date of occurrence, severity, treatment (if applicable), outcome, and assessments of the seriousness and causality. In addition, the Investigator must promptly document all device deficiencies on the *Device Deficiency* eCRF. The site must submit all available information on ADEs, SAEs, and device deficiencies to the Study Sponsor immediately as follows:

- **ADEs or SAEs are documented on the *Adverse Device Effect and Serious Adverse Event* eCRF within 24 hours of the Investigator's or site's awareness.**
- **Device deficiencies are documented on the *Device Deficiency* eCRF within 24 hours of the Investigator's or site's awareness. Please include a printed copy of the completed *Device Deficiency* eCRF with product returns.**
- **Additional relevant information after initial reporting is to be entered into the eCRF as soon as the data become available.**
- **Document any changes to concomitant medications on the appropriate eCRFs.**
- **All relevant documentation such as Discharge Summary, Autopsy Report, Certificate of Death etc, must be faxed to the Study Sponsor at [REDACTED]**

**NOTE:** Should the EDC system become non-operational, the site must complete the appropriate paper *Adverse Device Effect and Serious Adverse Event Form* or *Device Deficiency Form*. The completed form is faxed to the Study Sponsor at [REDACTED] within 24 hours of the Investigator's or site's awareness; however, the reported information must be entered into the EDC system once it becomes operational.

**Sponsor representatives and their contact information are provided in the Manual of Procedures that accompanies this protocol.**

Further, depending upon the nature of the AE or device deficiency being reported, the Study Sponsor may request copies of applicable portions of the subject's medical records. The Investigator must also report all AEs and device deficiencies that could have led to a SADE according to the requirements of regulatory authorities or IEC/IRB.

## 12.7.1 Intensity and Causality Assessments

For every AE in the study, the Investigator must assess the causality (Related or Not Related to the clinical investigation). An assessment of causality will also be performed by a Study Sponsor physician utilizing the same definitions, as shown below:

### 12.7.1.1 Causality

**Related** An AE may be classified as either definitely related or possibly related to the clinical investigation. Where a direct cause and effect relationship with the clinical investigation has not been demonstrated, but there is a reasonable possibility that the AE was caused by the clinical investigation, then causality should be assumed until it can be demonstrated that the AE is not related to the clinical investigation.

**Not Related** An AE classified as not related may either be definitely unrelated or simply unlikely to be related (ie, there are other more likely causes for the AE).

Where appropriate, the Investigator must assess the intensity (severity) of the AE as mild, moderate, or severe based on medical judgment with consideration of any subjective symptom(s), as defined below:

### 12.7.1.2 Intensity (Severity)

**Mild** An AE is mild if the subject is aware of but can easily tolerate the sign or symptom.

**Moderate** An AE is moderate if the sign or symptom results in discomfort significant enough to cause interference with the subject's usual activities.

**Severe** An AE is severe if the sign or symptom is incapacitating and results in the subject's inability to work or engage in their usual activities.

## 12.8 Unmasking of the Study Information

This study is not masked. However the examiner performing manifest refraction is masked to the refractive target and refractive error from the surgical planning and the operative visit.

## **12.9 Follow-Up of Safety Information**

The Investigator is responsible for adequate and safe medical care of subjects during the study and for ensuring that appropriate medical care and relevant follow-up procedures are maintained after the study. The Investigator must provide the Study Sponsor with any new safety information (which includes new AEs and changes to previously reported AEs) that may affect the safety evaluation of the device. Any additional data from these follow-up procedures performed up to 6 months after subject exit must be documented and available upon the Study Sponsor's request.

### **12.10 Pregnancy in the Clinical Study**

If a woman becomes pregnant during the study, this information must be documented by Medical Safety in the appropriate documentation. Pregnancy is not reportable as an AE; however, complications may be reportable and will be decided on a case-by-case basis. An Alcon prepared form will be utilized to capture all pregnancy-related information until birth of the child.

## **13 ANALYSIS PLAN**

### **13.1 Subject Evaluability**

The final subject evaluability will be determined prior to locking the database.

### **13.2 Analysis Data Sets**

#### **13.2.1 Safety Analysis Set**

All subjects with attempted IOL implantation (successful or aborted after contact with the eye) in at least one eye will be considered evaluable and included in the safety analysis set. The safety analysis set will be used for the safety analyses. Additionally, any AE experienced by a subject during the screening period will be presented separately in the safety analysis.

#### **13.2.2 All Implanted Analysis Set (AAS)**

All subjects with successful IOL implantation in the study eye will be included in the AAS. The primary analysis set for the primary and exploratory analyses will be the AAS.

#### **13.2.3 Best Case Analysis Set (BAS)**

BAS will include the subjects in AAS with the eye with the IOL which had

- at least 1 postoperative visit,
- no macular degeneration at any time; and
- no major protocol violation

The BAS is a supportive analysis set for the primary and exploratory analyses.

### 13.3 Demographics and Baseline Characteristics

Demographic and baseline characteristics will be summarized using frequency distributions for categorical parameters and descriptive statistics (number, mean, standard deviation, and median, minimum, maximum) for continuous parameters. Demographic characteristics will include age, gender, race and ethnicity.

Demographics and baseline characteristics summaries will be presented for the AAS for overall and by site.

### 13.4 Effectiveness Analyses

#### 13.4.1 Primary Effectiveness

The primary objective of this study is to demonstrate equivalency at each of the 3 clinical sites, between IOL SRK/T A-constant estimated based on postoperative manifest spherical equivalent refraction at 3 months and IOL SRK/T A-constant estimated based on postoperative spherical equivalent from autorefractometry using *Topcon KR-1W* at 3 months. The primary endpoints to be used for the primary analysis are:

- IOL SRK/T A-constant estimated based on the preoperative biometry, IOL power and postoperative manifest spherical equivalent refraction at 3 months and
- IOL SRK/T A-constant estimated based on the preoperative biometry, IOL power and postoperative spherical equivalent from autorefractometry using *Topcon KR-1W* at 3 months.

The primary analysis data set will be the AAS.

### 13.4.1.1 Statistical Hypotheses

The null and alternative hypotheses for the primary analysis are:

$$H_0: \mu(\text{diff}) \leq -0.15 \text{ or } \mu(\text{diff}) \geq 0.15$$

$$H_1: -0.15 < \mu(\text{diff}) < 0.15$$

Where  $\mu(\text{diff})$  refers to the mean difference between the endpoints listed in Section 13.4.1 for each site. This hypothesis will be assessed separately for each site with a paired t-test.

### 13.4.1.2 Analysis Methods

Two-sided 90% confidence interval will be constructed for the mean of the paired difference between the two estimated SRK/T A-constants separately for each site. If the two-sided 90% confidence interval fall within (-0.15, 0.15), then equivalence will be concluded.

Descriptive statistics (mean, median, standard deviation, number of eyes, minimum, maximum, and two-sided 90% confidence interval) will be provided for each site for the effectiveness endpoints and also for the difference.

### 13.4.2 Secondary Effectiveness

There are no secondary effectiveness analyses in this study.

#### 13.4.2.1 Statistical Hypotheses

Not Applicable

#### 13.4.2.2 Analysis Methods

Not Applicable

### 13.4.3

[Redacted]

[Redacted]

- [Redacted]

- [Redacted]
- [Redacted]
- [Redacted]
- [Redacted]

13.4.3.1

[Redacted]

[Redacted]

[Redacted]

13.4.3.2

[Redacted]

[Redacted]

[Redacted]

[Redacted]

[Redacted]

[Redacted]

[Redacted]

[Redacted]

[Redacted]

[Redacted]

### 13.5 Handling of Missing Data

All data obtained in evaluable subjects will be included in the analysis. No imputation for missing data will be carried out.

### 13.6 Multiplicity

No alpha adjustment will be applied for testing multiple hypotheses.

### **13.7 Safety Analysis**

The safety analyses will include the following safety assessments:

- Adverse events including SSIs
- Slit-lamp examination
- Dilated fundus examination
- Surgical problems
- Subjective PCO
- PC
- IOL observations
- IOL position change
- IOP
- Device deficiencies

Descriptive statistics generated for safety parameters will be based upon the type of parameter (ie, whether the data are categorical or continuous) being analyzed. For categorical parameters, the statistics used to summarize the data will include sample size, number in the category, and percent in the category. For continuous parameters, sample size, mean, median, standard deviation, minimum, and maximum will be presented

### **13.8 Interim Analyses**

No formal interim analyses are planned.

### **13.9 Adaptive Study Design**

No adaptations are planned in this study.

### **13.10 Sample Size Justification**

A minimum of 165 subjects will be enrolled to ensure at least 144 evaluable subjects (48 evaluable subjects per site) complete the study.

With 48 evaluable subjects per site, study has 90% chance to show that the mean difference in IOL A-constants calculated with postoperative manifest spherical equivalent refraction at 3 months and postoperative spherical equivalent from autorefraction at 3 months is within the

equivalence margin of  $\pm 0.15$  for each site assuming that the mean and the standard deviation (SD) of a paired difference are 0 and 0.35 respectively.

The SD of 0.35 is based on the SD of the difference in the estimated A-constant between the first and the second eyes in subjects implanted with ACRYSOF IQ Monofocal IOL [REDACTED] (ACRYSOF IQ ReSTOR Multifocal +2.5 D).

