Alcon - Business Use Only

Document: TDOC-0052874

Status: Effective

Effective Date: 01-Sep-2016

Version: 2.0; CURRENT; Most-Recent; Effective

Short Title:

Statistical Analysis Plan

ILQ732-I001 /

NCT02842151

Full Title:

Statistical Analysis Plan

ILQ732-I001

Protocol Title: Optimizing the Assessment of Refractive Outcomes after
Cataract Surgery and Implantation of a Monofocal IOL

Project Number: A01983

Protocol TDOC Number: TDOC- 0050597

Author:

[REDACTED]

[REDACTED]

Approvals: See last page for electronic approvals.

Job Notes:

This is the original (Version 1.0) Statistical Analysis Plan for this study. This version of the Statistical Analysis Plan is based on Version 1.0 of the study protocol.

Printed By:

Print Date:

Alcon - Business Use Only**Effective Date:** 01-Sep-2016**Document:** TDOC-0052874**Version:** 2.0; CURRENT; Most-Recent; Effective**Status:** Effective**Executive Summary:****Key Objectives:**

To demonstrate equivalency, at each of the 3 clinical sites, between IOL SRK/T A-constant (Retzlaff et al., 1990) estimated based on postoperative manifest spherical equivalent refraction at 3 months and IOL A-constant estimated based on postoperative spherical equivalent from autorefraction using *Topcon® KR-1W* at 3 months.

Decision Criteria for Study Success:

The study will be considered a success if, the primary objective is met.

A two-sided 90% confidence interval will be constructed for the mean of the paired difference between the two estimated SRK/T A-constants separately for each site. If all the two-sided 90% confidence intervals fall within (-0.15, 0.15), then equivalence will be concluded.

Alcon - Business Use Only

Effective Date: 01-Sep-2016

Document: TDOC-0052874

Version: 2.0; CURRENT; Most-Recent; Effective

Status: Effective

5.3.3	Surgical Problems	14
5.3.4	Intraocular Pressure.....	14
5.3.5	Slit Lamp Examination	14
5.3.6	IOL Observations	14
5.3.7	IOL Position Change.....	14
5.3.8	Subjective Posterior Capsule Opacification.....	15
5.3.9	Posterior Capsulotomy.....	15
5.3.10	Dilated Fundus Examination.....	15
5.4	Interim Analysis for Safety	15
6	Analysis Strategy for Other Endpoints.....	15
7	Sample Size and Power Calculations	15
8	References	16
9	Deviations from Protocol	16
10	Revision History.....	16

List of Tables

Table 1-1	Schedule of Study Visits	6
-----------	--------------------------------	---

List of Figures

[figure not shown]
Figure 4-1	Cumulative Line Plot	11

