4.3 Statistical Methods for Efficacy Analyses

The primary hypothesis will be tested by generating a 2-sided 90% confidence interval for the paired difference at each site. Equivalence will be declared if the bounds of the 90% CI are contained within the equivalence range (-0.15, 0.15). SAS PROC TTEST will be used to generate the confidence interval based on the pseudo code below:

```
proc ttest data=Aconst alpha=0.1;  
  paired AconstMR*AconstAR;  
run;
```

Additionally, as a sensitivity analysis, a mixed effects model will be fit to estimate overall effect of refraction method as well as by site. The pseudo code is provided below:

```
proc mixed data=Aconst;  
  class subj RefMethod Site;  
  model SBP=RefMethod|site;  
  repeated RefMethod / subject=subj type=un;  
  lsmeans RefMethod*site/diffs cl ;  
run;
```

Descriptive statistics (mean, median, standard deviation, number of eyes, minimum, maximum, and two-sided 90% confidence interval) will be provided for each site for the A-constants calculated using manifest refraction and autorefraction and also for the difference.

[figure not shown]
Alcon - Business Use Only

Effective Date: 01-Sep-2016

Document: TDOC-0052874

Version: 2.0; CURRENT; Most-Recent; Effective

Status: Effective

Printed By:

Print Date:

[figure not shown]
Alcon - Business Use Only

Effective Date: 01-Sep-2016

Document: TDOC-0052874

Version: 2.0; CURRENT; Most-Recent; Effective

Status: Effective

Printed By:

Print Date:

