4.4 Multiplicity Strategy

No multiplicity adjustments are planned for primary or exploratory analyses. The primary hypothesis tests must be rejected at every site for the study to be considered a success.

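### The stated 90% power does not follow from the planned equivalence rule, which gives about 80% at each site and about 51% that all three sites pass

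*Protocol*

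**What the plan says.** Protocol 13.10 gives the sample size as follows: "A minimum of 165 subjects will be enrolled to ensure at least 144 evaluable subjects (48 evaluable subjects per site) complete the study". It then states the power: "With 48 evaluable subjects per site, study has 90% chance to show that the mean difference in IOL A-constants" is within ±0.15 "for each site assuming that the mean and the standard deviation (SD) of a paired difference are 0 and 0.35 respectively". Protocol Section 3 and SAP Section 7 make the same claim. None of the three places gives a formula.

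The decision rule at a site is in Protocol 13.4.1.2: "If the two-sided 90% confidence interval fall within (-0.15, 0.15), then equivalence will be concluded". Protocol 13.4.1.1 adds: "This hypothesis will be assessed separately for each site with a paired t-test". The SAP 4.3 code agrees, with "proc ttest data=Aconst alpha=0.1" on paired data.

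The rule for the study as a whole is in the SAP. Its executive summary says: "If all the two-sided 90% confidence intervals fall within (-0.15, 0.15), then equivalence will be concluded". SAP 4.4 says: "The primary hypothesis tests must be rejected at every site for the study to be considered a success". The protocol states the objective as equivalence at each of the three sites, but it has no separate study-success rule.

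**The concern.** A 90% interval lies inside the margin only if its lower bound is above -0.15 and its upper bound is below 0.15. Each condition is a one-sided 5% test. When the true difference is 0, each test fails about equally often, so the chance of failing at least one of them is about twice the chance of failing a given one. A sample size that gives 90% power for one bound gives only about 80% for the interval rule. Requiring all three sites to pass lowers the probability of success again.

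The power statement is the only justification given for the sample size. If it is wrong, the sponsor and the ethics committees are relying on a chance of success that the design does not have. A site whose interval crosses the margin could also be taken as a sign that the methods differ there, when under this design such a result is quite likely even if they agree exactly.

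**Working it through.** **Inputs.** n = 48 paired differences per site, mean 0, SD 0.35 and margin 0.15 (Protocol 13.10, SAP 7). Two-sided 90% interval from a paired t-test, so one-sided alpha 0.05 on each side with 47 degrees of freedom (Protocol 13.4.1.1 and 13.4.1.2, SAP 4.3). Three sites, all required to pass (SAP executive summary and 4.4).

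**Standard error.** SE = 0.35/√48 = 0.0505. Margin/SE = 0.15/0.0505 = 2.969.

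**Reproducing the stated 90%.** For a single one-sided paired t-test at 5%, power = P(T > t₀.₉₅,₄₇), where T is noncentral t with 47 degrees of freedom and noncentrality 2.969. The result is 0.8999. The normal approximation, Φ(2.969 − 1.645), gives 0.907. One bound on its own therefore reproduces the stated figure.

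**Power of the planned rule at one site.** Both bounds must clear the margin:

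- Normal approximation: 2Φ(2.969 − 1.645) − 1 = 2 × 0.9073 − 1 = 0.815.
- Exact, integrating over the distribution of the sample SD: 0.7999. Since failing at both bounds together is negligible here, this equals 2 × 0.8999 − 1 to the accuracy shown.
- Simulation of 200,000 trials: 0.799 for the interval rule and 0.899 for the single bound.

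**Power for study success.** The sites enrol different subjects, one eye each, so independence is reasonable: 0.7999³ = 0.512. The normal approximation gives 0.8146³ = 0.541.

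**Other rules that might explain 90%.** Two one-sided tests at 10% each (an 80% interval) give 0.903, but that is not the planned interval. Two tests at 2.5% each give 0.657. One pooled test of all 144 subjects gives 0.9995. Single one-sided tests passing at all three sites give 0.8999³ = 0.729.

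**Sensitivity to the SD** (n = 48, mean 0):

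| SD | Per site | All three |
|---|---|---|
| 0.25 | 0.986 | 0.958 |
| 0.30 | 0.923 | 0.786 |
| 0.35 | 0.800 | 0.512 |
| 0.40 | 0.640 | 0.262 |
| 0.45 | 0.472 | 0.105 |

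At n = 48, 90% per site needs an SD of about 0.31, and 90% jointly needs about 0.27.

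**Sensitivity to the true mean.** A true difference of 0.05 (an assumption, not a figure from the plan) gives 0.608 per site and 0.608³ = 0.225 for all three.

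**Sample size under the plan's own inputs** (SD 0.35, mean 0):

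| Evaluable per site | Total | Per site | All three |
|---|---|---|---|
| 48 | 144 | 0.800 | 0.512 |
| 55 | 165 | 0.865 | 0.646 |
| 61 | 183 | 0.904 | 0.739 |
| 67 | 201 | 0.932 | 0.810 |
| 79 | 237 | 0.967 | 0.904 |

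**The case against.** The strongest points on the other side concern scope and certainty rather than the arithmetic.

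- **The source of the 90% is not documented.** This stands. A single one-sided test fits almost exactly, but two tests at 10% each also round to 90%. The mismatch with the planned rule is certain; its cause is inferred.
- **The sentence reads most naturally as per-site power, so 51% contradicts no stated figure.** This is fair. The per-site figure is an error; the joint figure is an omission. The omission still matters, because the SAP defines success by the joint rule.
- **The SD may not be 0.35.** It comes from differences between first and second eyes, not from two refraction methods on the same eye, and both endpoints share the same preoperative biometry and IOL power. The relevant SD could therefore differ, in a direction the documents do not settle. But the plan's claim is conditional on 0.35, and under that condition it is wrong.
- **48 is a floor, with about 55 per site targeted.** Even if all 55 were evaluable, power would be 86.5% per site and 64.6% jointly.
- **Requiring every site to pass needs no alpha adjustment.** This is correct. Type I error is protected, and the cost falls entirely on power.
- **Misreading of a failed site is speculative.** This is also fair. The plan reports each site's interval and descriptive statistics, and adds a mixed-model sensitivity analysis, so a careful reader could see that a result was merely imprecise.

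**Conclusion.** The concern holds. With 48 evaluable subjects, mean difference 0 and SD 0.35, the planned interval rule has 80.0% power at a site, against the 90% stated. No reading of the sentence rescues it: per-site power is 80%, and the probability that all three sites pass is about 51%. The per-site result uses only the plan's inputs and normally distributed differences. The joint result also assumes independent sites that share the same SD and a zero true difference. A zero difference is the most favourable case; any real difference between the methods lowers both figures. The validity of the test and its type I error are not affected.

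**What to change.** Replace the power statement in Protocol Section 3, Protocol 13.10 and SAP 7 with wording such as: *With 48 evaluable subjects per site, a true mean paired difference of 0 and an SD of 0.35, the power to conclude equivalence is about 80% at each site. Assuming independent sites, the probability that all three sites meet the criterion is about 51%.* State the method used (two one-sided paired t-tests at 5% each). Add power over a range of SDs such as 0.25 to 0.45, and note that 0.35 comes from between-eye differences.

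The cost is wording only: no added patients and no change to the margin, alpha, test or success rule. The stated power becomes less favourable, and restating it does not raise it. If the sponsor wants 90% under its own assumptions, it needs 61 evaluable per site (183 in total) for per-site power or 79 per site (237 in total) for joint power. At the plan's 13% discontinuation rate, that means about 183/0.87 = 211 or 237/0.87 = 273 eligible subjects, compared with 165 now. The 183 evaluable subjects should not be confused with the 183 expected enrolments in Protocol Section 9, which are counted before screen failures and discontinuations.

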	
Descriptive statistics for AEs will be presented separately.
 
Sample Size Justification: A minimum of 165 subjects will be enrolled to ensure at least 144 evaluable subjects (48 evaluable subjects per site) complete the study.
 
With 48 evaluable subjects per site, study has 90% chance to show that the mean difference in IOL A-constants calculated with
 
 
• post-op manifest spherical equivalent refraction at 3 months vs.
 
• post-op spherical equivalent from autorefraction using Topcon KR-1W at 3 months
 
 
is within the equivalence margin of <math>\pm 0.15</math> for each site assuming that the mean and the standard deviation of a paired difference are 0 and 0.35 respectively.
 
Standard deviation of 0.35 is based on the standard deviation of the difference in A-constant between the first and the second eye in subjects implanted with ACRYSOF IQ Monofocal IOL [REDACTED] [REDACTED] (ACRYSOF IQ ReSTOR® Multifocal +2.5 D).

Key Words for Posting in Registries
	
Prospective, interventional, multi-center study; being conducted in the US and Ireland; 183 enrolled 144 completed subjects

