## **6 INTRODUCTION**

### **6.1 Rationale and Background**

Following cataract surgery, there is a distribution in refractive outcomes relative to the intended refractive target (typically emmetropia). The refractive outcome distribution will have a mean offset (relative to target) as well as some finite spread (eg, standard deviation). Previously we have analyzed the spread in outcomes (for standard-of-care surgery) using an “error budget” analysis. This analysis provides the following estimated for refractive outcome variance (ie, the square of the standard deviation in spherical equivalent error):

- Postoperative refraction – 25.6%
- IOL placement (axial position, decentration, tilt) – 16.8%
- Cornea anterior asphericity – 16.8%
- Cornea posterior/anterior radius ratio – 11.4%
- Corneal anterior radius measurement – 9.8%
- IOL step size – 5.8%
- Cornea refractive index – 4.7%
- Axial length measurement – 3.7%
- IOL manufacturing tolerance – 2.1%
- Vitreous refractive index – 2.1%
- Aqueous refractive index – 0.9%
- Cornea posterior asphericity – 0.2%
- Cornea thickness – 0.1%

The results from the analysis show that:

- Noise in the postoperative refraction is a major contributor
- Uncertainty in the IOL location in the eye is also a large component
- Most of the remaining contributors relate to inadequate preoperative characterization of the eye

Conventional clinical wisdom holds that each surgeon will have unique outcomes due to factors particular to their surgical technique, inherent clinic measurement practices and equipment. The general concept is that surgical technique and in some instances

complications will impact the final resting location of the IOL. Other site-specific factors such as biometry device calibration or postoperative refraction procedure specifics could also influence the offset. Surgeons are encouraged to track outcomes and minimize the offset by “personalizing” the IOL power equation constant(s) related to the IOL position (eg, the “A-constant”) (Gale 2009). This requires analyzing preoperative biometry, implanted lens power, and postoperative refraction (typically collected from manifest refraction) for a population of 50+ eyes per IOL model (Sheard 2014). Changes in the A-constant of 0.15 D or less are not considered clinically significant, based on the impact on refractive outcome distributions (Aristodemou 2011).

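### The planning SD of 0.35 is an unjustified between-eye proxy for a same-eye difference, and even at 0.35 the planned equivalence rule has 80% power per site, not the stated 90%

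*Protocol*

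**What the plan says.** Protocol 13.10 gives 90% power with 48 evaluable subjects per site and a margin of ±0.15, "assuming that the mean and the standard deviation (SD) of a paired difference are 0 and 0.35 respectively". It then gives the origin of the SD: "The SD of 0.35 is based on the SD of the difference in the estimated A-constant between the first and the second eyes in subjects". SAP 7 repeats this, and the Protocol 3 summary says the same: "Standard deviation of 0.35 is based on the standard deviation of the difference in A-constant between the first and the second eye". Part of the source sentence is redacted; nothing here is held against the plan on that account.

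The primary analysis (Protocol 13.4.1.2) is this: "Two-sided 90% confidence interval will be constructed for the mean of the paired difference between the two estimated SRK/T A-constants separately for each site". The decision rule follows: "If the two-sided 90% confidence interval fall within (-0.15, 0.15), then equivalence will be concluded". SAP 4.3 fixes the pair in its code as "paired AconstMR*AconstAR", that is, manifest refraction against autorefraction. Protocol 8.1 enrols one eye per subject. Under Protocol 13.4.1 both A-constants use the same preoperative biometry and IOL power; only the postoperative refraction differs. The SAP Executive Summary and SAP 4.4 require equivalence at every site for the study to succeed.

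**The concern.** Two separate things are wrong with the stated power.

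**The SD belongs to another variable.** A first-eye-minus-second-eye difference carries whatever differs between two eyes: lens position, corneal and axial-length error, lens tolerance, and refraction error in each eye. In a same-eye difference between methods, the eye, its biometry and its lens are common to both A-constants and essentially cancel. What remains is manifest error, KR-1W error and any eye-specific disagreement between the two methods. As described, the between-eye figure says nothing about how much noisier the KR-1W might be, or about method disagreement. The readable text offers no argument linking one SD to the other.

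**The 90% does not match the planned rule.** Requiring the whole interval to lie inside (-0.15, 0.15) means passing two one-sided tests. A power calculated for only one of them is too high.

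At stake is whether the stated chance of success, per site and for the study, describes this design.

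**Working it through.** **Inputs.** n = 48 per site, mean 0, SD 0.35 (Protocol 13.10, SAP 7); margin ±0.15 and two-sided 90% interval (Protocol 13.4.1.2); all three sites must pass (SAP 4.4).

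**Step 1: reproduce the 90%.**
- Standard error = 0.35/√48 = 0.0505; margin/standard error = 0.15/0.0505 = 2.97.
- One one-sided t-test at 0.05 (noncentral t, 47 df): power 0.8999. Normal approximation: Φ(2.97 − 1.645) = 0.907.

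The stated 90% is therefore the power of a single one-sided test.

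**Step 2: power of the planned rule.** Equivalence requires |mean difference| < 0.15 − t(0.95, 47)·s/√48. Integrating over the distribution of the sample SD s gives 0.7999. As a check, when the mean is 0 and each one-sided test fails with probability 1 − 0.8999, power is close to 2 × 0.8999 − 1 = 0.7998. The normal approximation gives 0.815, and a simulation of 400,000 trials gave 0.801. Power per site is thus 80.0%, and at SD 0.35 the rule would need 61 per site for 90%.

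**Step 3: all three sites.** Taking sites as independent, 0.7999³ = 0.512.

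**Step 4: dependence on the SD** (planned rule, n = 48, mean 0; the SD range is an assumption, because the documents give no same-eye SD).

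| Same-eye SD | Per site | All three sites |
|---|---|---|
| 0.25 | 98.6% | 95.8% |
| 0.30 | 92.3% | 78.6% |
| 0.35 | 80.0% | 51.2% |
| 0.40 | 64.0% | 26.2% |

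Solving for 90% per site gives an SD of 0.311.

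**Step 5: which way could the proxy err?** This is an illustration only. Protocol 6.1 lists "Postoperative refraction – 25.6"% of refractive outcome variance, which leaves 74.4% for other sources. Assume these shares carry over to the A-constant, that all other sources cancel within an eye, and that refraction errors are independent between eyes. Let r be the between-eye correlation of the A-constant and v the ratio of KR-1W to manifest noise variance. The documents give neither. With s² the A-constant variance:
- between-eye variance: 0.35² = 2s²(1 − r)
- same-eye variance: 0.256·s²(1 + v)
- same-eye SD = 0.35·√[0.256(1 + v)/(2(1 − r))]

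| v | r | Same-eye SD | Power per site |
|---|---|---|---|
| 1 | 0 | 0.177 | >99.9% |
| 1 | 0.5 | 0.250 | 98.5% |
| 1 | 0.744 (maximum) | 0.350 | 80.0% |
| 2 | 0.5 | 0.307 | 91.0% |
| 3 | 0.5 | 0.354 | 78.7% |
| 2 | 0.744 | 0.429 | 54.3% |

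If the KR-1W is no noisier than manifest refraction (v ≤ 1), 0.35 is never too small under this model. If it is noisier, 0.35 may be too small, depending on r.

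**The case against.** The plan discloses the source of the SD in all three places and states the power conditionally. A reader might infer that the power simply does not apply to the primary test. That is too strong: a proxy leaves the assumption unverified but does not make a conditional calculation inapplicable.

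A reader might also infer that 0.35 omits the tested component altogether. It does not. A between-eye difference in refraction-derived A-constants carries refraction error from both eyes; what it fails to capture is excess KR-1W noise and eye-specific method disagreement. With equal noise in the two methods, 0.35 is conservative or at worst exact under the Step 5 model, so the documents do not support a claim that the trial is underpowered because of the proxy.

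Nor would a failed site be impossible to explain. Protocol 13.4.1.2 and SAP 4.3 already report the mean, SD and 90% interval of the same-eye difference by site, which separates a shifted mean from a wide interval. The planning SD affects neither the decision rule nor its type I error.

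Finally, it is tempting to call an SD range supported by the error budget in Protocol 6.1. That section gives variance shares only: no absolute SD, no between-eye correlation and no KR-1W term.

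These points limit the SD criticism to a missing justification of unknown direction. They do not touch the second part: accepting SD 0.35 in full, the planned rule still has 80.0% power per site.

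**Conclusion.** The point stands in two parts.

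1. The SD of 0.35 is a between-eye proxy with no stated justification for the same-eye manifest-minus-KR-1W difference. The direction of error is unknown, and the figure may be conservative.
2. The stated 90% is wrong as written for the planned rule, wherever the SD came from. It overstates per-site power by 10 percentage points. If the claim is read as covering all three sites together, the comparison is 90% against about 51%.

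The 80.0% rests on normally distributed differences, a true mean of 0 (the most favourable case) and SD 0.35. The 51% also assumes independent sites. The SD range in Step 4 is an assumption, not an estimate, and Step 5 is illustrative. If the true same-eye SD is about 0.31 or less, 90% per site is reached with the present sample size.

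**What to change.** In Protocol 3, Protocol 13.10 and SAP 7:
- Label 0.35 as a between-eye proxy. Say that it includes between-eye variance that cancels in the same-eye test and does not capture excess KR-1W noise or eye-specific disagreement between methods.
- Replace the 90% with the Step 4 table: power of the planned 90% interval rule at n = 48, per site and for all three sites, with the SD range stated as an assumption and site independence stated for the joint column.
- State that 90% per site needs a same-eye SD of about 0.31 or less.

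The sample size, test, margin and procedures do not change. No extra SD check at Visit 1 is needed: the 3-month same-eye SD is already planned, and Protocol 7.1 names 3 months as the point of refractive stability. The cost is a few sentences and one small table. The downside is that the stated power becomes less favourable.
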